3. STUDY OVERVIEW

Start of the study: in North and Latin America: [REDACTED]

in Europe: [REDACTED]

End of the study: the study is expected to be concluded upon final collection of data for all outcome measures and adverse events, including safety follow up (last participant's last visit).

Subjects in this randomized, double-blind, placebo controlled, parallel-group, multiple-center study will be assigned to treatment with the investigational products or placebo control according to a randomization scheme and titration schedule.

- **Part I:** 16 weeks; Subjects will be randomized to placebo, Low dose [REDACTED] Intermediate dose [REDACTED] [REDACTED] or High dose [REDACTED] of SCD-044 [REDACTED]
[REDACTED]
[REDACTED]
[REDACTED] to assess primary and secondary endpoints at Week 16
- **Part II:** Week 16 to Week 28:
At Week 16, subjects initially randomized to a treatment group will be re-randomized or discontinued from the study based on the PASI response as follows:
 - Subjects initially randomized to placebo with a response of:

[REDACTED] will be re-randomized to Intermediate dose, High dose, [REDACTED]
[REDACTED] respectively
[REDACTED] : will be re-randomized to Intermediate dose or High dose [REDACTED]

[figure not shown]
- Subjects originally randomized to Low dose and Intermediate dose arms with a response of:
[REDACTED] will be switched to High dose [REDACTED],
[REDACTED]
[REDACTED] : will remain on their assigned dosing regimen

- Subjects originally randomized to High dose arm with a response of:
[REDACTED]
[REDACTED] : will remain on their assigned dosing regimen

[REDACTED]
[REDACTED]
[REDACTED]
[REDACTED]
[REDACTED]
[REDACTED].

Re-randomized subjects continuing in the study will stay on their assigned dosing regimen until the end of Part II (Week 28). [REDACTED]
[REDACTED]

- **Part III:** Week 28 to Week 52: Subjects with a response of [REDACTED] at Week 28 will be discontinued from the study. Subjects with a response of [REDACTED] at Week 28 will continue their existing dosing regimen until the end of Part III.

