10. A blood sample(s) will be collected for Hematology, Chemistry, and Coagulation profile (See Section 5.5)
11. A blood sample will be collected for PD biomarkers sample (See Section 6.3)
12. A blood sample will be collected within one hour before dosing for PK testing (See Section 6.2)
13. A blood sample will be collected for C-reactive protein (CRP) – (See Section 5.5)
14. Vital signs (blood pressure, pulse, respiratory rate and oral body temperature) will be documented. Subjects must remain in a seated or supine position for at least 5 minutes before vital signs are obtained. (See Section 5.3)

If Subject eligible to continue the study drug dosing based on PASI response ≥75

15. Independent Safety Assessor review:
 - Safety Lab Alerts
 - [REDACTED]
 - As available
 - i. Lab results
 - ii. Exam results
16. Study drug administration in a clinic before 12 noon (See Section 8.5)
17. The following will be dispensed during Visit 16:
 - The study drug assembled for Visit 16
 - A diary card with instructions and to record the study drug use, health changes and concomitant medication
18. A general safety review before discharge
19. [REDACTED]
[REDACTED]
[REDACTED]

If Subject discontinue from the study drug dosing based on PASI response <75 (the visit is to be reported as End of Treatment)

15. Independent Safety Assessor review:
 - Safety Lab Alerts
 - [REDACTED]
 - As available
 - i. Lab results
 - ii. Exam results
16. The following will be dispensed during Visit 16:
 - a. A diary card with instructions and to record health changes and concomitant medication
17. A general safety review before discharge

Confidential

18. [REDACTED]
[REDACTED]

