### **6.1.1 Treatment Groups**

Data collected up to Week 16 visit will be analyzed by treatment groups based on the subject’s treatment in Part I of the study:

- Placebo

- SCD-044 [REDACTED]
- SCD-044 [REDACTED]
- SCD-044 [REDACTED]

Efficacy data collected after Week 16 visit (i.e., Parts II-IV), as well as disposition and compliance in Parts II-IV, will be analyzed by treatment groups based on the responder status at the end of Part I (Week 16) (i.e.,  $\geq$  PASI50 or  $<$  PASI50), the subject's treatment in Part I and the subject's treatment in Part II of the study:

- Part I Responders
  - Placebo/SCD-044 [REDACTED]
  - Placebo/SCD-044 [REDACTED]
  - SCD-044 [REDACTED]
  - SCD-044 [REDACTED]
  - SCD-044 [REDACTED]
- Part I Non-Responders
  - Placebo/SCD-044 [REDACTED]
  - Placebo/SCD-044 [REDACTED]
  - SCD-044 [REDACTED]
  - SCD-044 [REDACTED]

Safety data collected after Week 16 visit (i.e., Parts II-IV) will be analyzed by treatment groups based on the subject's treatments in Part I and in Part II:

- Placebo/SCD-044 [REDACTED]
- Placebo/SCD-044 [REDACTED]
- SCD-044 [REDACTED]

Adverse events and concomitant medications will be additionally analyzed for the entire study. Details are provided in the sections 6.11.1 and 6.11.6.

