1. For events in Part I only, using Part I treatment groups, with the additional groups SCD-044 Any Dose (including the three SCD-044 groups) and Total (including all subjects).
2. For events in Parts II/III/IV only, using Parts II/III/IV safety treatment groups, with the additional group Total.

3. For the entire study using only the subjects who stayed on the same treatment throughout the study, using the three active treatment groups with the additional group Total.

An overall summary for the Safety population will include, by treatment and overall, the number and percentage of subjects reporting at least 1 TEAE in the following categories:

- Any TEAE
- Treatment-related TEAE
- Serious TEAE
- Serious drug-related TEAE
- TEAE leading to discontinuation of the study medication
- Treatment-related TEAE leading to discontinuation of the study medication
- TEAE requiring temporary interruption of the study medication
- Treatment-related TEAE requiring temporary interruption of the study medication
- TEAE leading to death.
- TEAEs of special interest

Additional overall summary of cardiovascular TEAEs will include, by treatment and overall, the number and percentage of subjects reporting at least one cardiovascular TEAE in the following categories:

- Any cardiovascular TEAE
- Treatment-related cardiovascular TEAE
- Serious cardiovascular TEAE
- Cardiovascular TEAE leading to discontinuation of the study medication
- Cardiovascular TEAE leading to death.
- Cardiovascular TEAEs of special interest
- Cardiac arrhythmias

The following TEAE frequency tables will be prepared summarizing the number and percentage of subjects reporting at least one TEAE by MedDRA System Organ Class (SOC) and preferred term PT, by treatment group for the Safety population:

- All TEAEs
- Serious TEAEs
- Treatment-related TEAEs
- Serious treatment-related TEAEs
- TEAEs leading to discontinuation of the study medication
- Treatment-related TEAEs leading to discontinuation of the study medication
- TEAE requiring temporary interruption of the study medication
- Treatment-related TEAE requiring temporary interruption of the study medication
- TEAEs occurring in  $\geq 2\%$  in any treatment group
- TEAEs of special interest
- Cardiac arrhythmias
- TEAEs with onset during the [REDACTED] period in Part I and in Part II
- TEAEs by Severity

- TEAEs by Relationship to Study Drug.

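### Parts II–IV adverse events are tabulated only as crude percentages, although PASI response at Week 28 decides whether a subject is observed for about 16 or about 40 weeks; for events that keep accruing, a more effective regimen can look worse at the same rate

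*SAP*

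**What the plan says.** SAP 6.11.1 presents AEs in three ways. Presentation 1 covers Part I by randomised arm. Presentation 2 is "For events in Parts II/III/IV only, using Parts II/III/IV safety treatment groups, with the additional group Total". Presentation 3 is "For the entire study using only the subjects who stayed on the same treatment throughout the study". The overall summary reports "the number and percentage of subjects reporting at least 1 TEAE in the following categories", and the cardiovascular summary and the tables by system organ class and preferred term use the same measure.

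SAP 6.1.1 sets the later safety groups: "Safety data collected after Week 16 visit (i.e., Parts II-IV) will be analyzed by treatment groups" defined by the Part I and Part II treatments. Unlike the efficacy groups, they are not split by Week 16 responder status.

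Protocol 7.1.9 has two branches at Week 28. One reads "If Subject eligible to continue the study drug dosing based on PASI response ≥75"; the other reads "If Subject discontinue from the study drug dosing based on PASI response <75 (the visit is to be reported as End of Treatment". Part III runs from Week 28 to Week 52 (Protocol 3). Follow-up lasts four weeks after the last dose (Protocol 3, Part IV), and AEs are collected up to the follow-up visit (Protocol 10.6).

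Exposure is handled apart from AEs. SAP 6.7.1 summarises its duration by group and study part, SAP 6.11.1 lists onset days, and Protocol 9.7 adds AEs by actual dose at onset. The visible text of both documents plans no AE analysis by person-time or time to first event.

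**The concern.** A crude percentage compares groups fairly when they are watched for similar lengths of time. After Week 16 they are not, and what decides the length is the efficacy outcome. A regimen that brings more subjects to the Week 28 threshold keeps more of them on drug and under AE collection for a further 24 weeks. Any event with a continuing risk then has more time to appear in that group.

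This is a dose-ranging study, and the visible safety groups after Week 16 contain no continuing placebo arm. The long-term AE comparison is therefore between regimens. The events most exposed to the problem are those that can arise at any time. Protocol 5.9 lists serious infections, new malignancy, macular edema, PML and PRES as events of special interest, and Protocol 4.6 names infection as a class risk. A reader of presentation 2 could take longer observation for a higher rate.

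**Working it through.** The documents state no AE rate and no expected Week 28 response, so there is no planned figure to reproduce. The windows come from the documents; the rates and continuation shares are assumptions.

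**Windows from the start of Part II**
- PASI response below 75 at Week 28: (28 − 16) + 4 = 16 weeks.
- PASI response of 75 or more: (52 − 16) + 4 = 40 weeks.

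**Formula.** Let a first event have the same constant rate λ per week in both groups, let c be the share continuing past Week 28, and ignore other dropout. Then

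crude % = (1 − c)(1 − exp(−16λ)) + c(1 − exp(−40λ)).

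**Example.** At 50 per 100 subject-years, λ = 0.50 / 52.18 = 0.00958 per week. The two terms are 1 − exp(−0.153) = 14.2% and 1 − exp(−0.383) = 31.8%.
- c = 30%: 0.7 × 14.2 + 0.3 × 31.8 = 19.5%; mean observation 0.7 × 16 + 0.3 × 40 = 23.2 weeks.
- c = 60%: 0.4 × 14.2 + 0.6 × 31.8 = 24.8%; mean observation 0.4 × 16 + 0.6 × 40 = 30.4 weeks.

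**Range, 30% against 60% continuing**

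| True rate per 100 subject-years | Crude % at c = 30% | Crude % at c = 60% | Gap (points) |
|---|---|---|---|
| 20 | 8.4 | 10.9 | 2.5 |
| 50 | 19.5 | 24.8 | 5.3 |
| 100 | 34.5 | 42.7 | 8.1 |
| 200 | 55.6 | 65.4 | 9.8 |

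Over rates of 5 to 400 per 100 subject-years, the gap is 0.4 to 6.5 points for 20% against 40% continuing, and 0.9 to 13.0 points for 20% against 60%.

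**Does a rate repair it?** At a true rate of 100 per 100 subject-years, first events divided by time at risk return 100 in both groups. Crude incidence over the fixed 12 weeks from Week 16 to Week 28 is also equal in both: 1 − exp(−12λ) = 10.9% at 50 and 20.5% at 100.

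**Where a rate alone fails.** Suppose 20% of subjects have an event in the first three weeks (on average at 1.5 weeks) and none later. Crude incidence is 20% in both groups. Time at risk per subject is 0.8 × 23.2 + 0.2 × 1.5 = 18.9 weeks against 0.8 × 30.4 + 0.2 × 1.5 = 24.6 weeks. The rates are then 55.3 and 42.4 per 100 subject-years, which flatters the longer-treated group.

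**Whole-study tables.** Windows are 20, 32 or 56 weeks for stopping at Week 16, 28 or 52. Assume 50 per 100 subject-years. For Low-dose stayers, assume 40% continue past Week 28. For High dose, assume 60% pass Week 16, and 70% of those continue past Week 28.
- Low: mean 0.6 × 32 + 0.4 × 56 = 41.6 weeks; 32.5%.
- High, subjects stopped at Week 16 left out: mean 0.3 × 32 + 0.7 × 56 = 48.8 weeks; 37.0%.
- High, those subjects included: mean 0.4 × 20 + 0.6 × 48.8 = 37.3 weeks; 29.2%.

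The sign of the difference turns on a membership rule that the SAP does not state. That some High-dose non-responders stop at Week 16 is inferred from SAP 6.1.1 and 6.2, because the protocol text on that arm is redacted.

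**The case against.** The strongest reply is that the main safety comparison is sound. Presentation 1 compares all three doses with placebo, as randomised, over one planned 16-week period. SAP 6.11.1 also tabulates events week by week in the first weeks of Part I and Part II, and those short common windows are not affected by the Week 28 rule. A reader can see unequal exposure in the SAP 6.7.1 summaries. The table shells are in a separate document that was not available. All of this stands. It does not cure the denominator, because mean exposure beside a percentage does not give a first-event rate by category.

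A second reply is that most groups after Week 16 are not comparable anyway. Stayers and switchers are selected by Week 16 response, and adjusting for time does not undo that. This also stands. The cleanest contrast is between the Placebo/SCD-044 groups, which are re-randomised to different doses. With about 60 placebo subjects (240 / 4), and an equal split assumed, each has at most about 30. The standard error of 24.8% minus 19.5% is then √(0.195 × 0.805/30 + 0.248 × 0.752/30), about 11 points, or twice the 5.3-point gap. The distortion is modest beside the noise, but it is systematic and avoidable.

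A reader might also infer that a more effective dose is bound to look less safe in every later table. The documents do not support that. It needs events that continue to accrue after Week 28, and in presentation 3 the direction can reverse.

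**Conclusion.** The concern holds for presentation 2, within limits. Planned observation after Week 16 is about 16 or 40 weeks according to Week 28 response, and the visible tables make no allowance for it. For events with a continuing risk, the more effective regimen can show a higher crude percentage at the same rate: 19.5% against 24.8% in the central example, with gaps from under 1 point to 13 points across the assumptions tried. Only the windows are documented. The sizes rest on a constant and equal hazard, assumed continuation shares, and no other dropout.

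The Week 28 rule does not touch events confined to the weeks before it, or the Part I tables. For presentation 3 no direction can be claimed. Switchers leave that table, and the SAP does not say whether subjects stopped at Week 16 or Week 28 count as having kept one treatment.

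It would be going too far to conclude that a planned inference fails or that dose choice is necessarily misled. These tables are descriptive, Protocol 9.7 plans no inferential safety analysis, and the placebo-controlled Part I comparison remains available. The change is a worthwhile, inexpensive improvement to the long-term safety comparison.

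**What to change.** In SAP 6.11.1:

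1. In presentations 2 and 3, keep the crude counts and add subjects with a first event per 100 subject-years at risk, with 95% CI, for any TEAE, serious TEAEs, TEAEs leading to discontinuation, events of special interest, cardiovascular events and infections. Time at risk should run to the first event or the end of AE collection, so that follow-up weeks count in the denominator as they do in the numerator.
2. For presentation 2, add a crude incidence table for the fixed Week 16–28 window.
3. For presentation 3, state whether subjects stopped at Week 16 or at Week 28 belong to the set.
4. Leave Part I as it is.

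The cost is SAP wording and a few extra tables. AE onset dates and last-dose dates are already collected (SAP 6.7.1 and 6.11.1), so no new data or protocol change is needed. The downside is that the rates assume a roughly constant hazard and can flatter the longer-treated group when events come early. That is why the fixed-window table should accompany them. Neither table removes the response-based selection of stayers and switchers, and a footnote should say so.

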#### 6.11.2 Laboratory tests

A central laboratory will be used for all assessments unless noted otherwise. Unscheduled laboratory assessments can be performed at discretion of the Investigator in response to AEs. The laboratory assessments include:

**Hematology:** at all study visits a blood sample will be collected for total and differential WBC count, Absolute Neutrophil count (ANC), ALC, Platelet count, Hemoglobin, Hematocrit, Mean Corpuscular Volume (MCV) testing. Additionally, total WBC count with differential counts including ALC and ANC counts will be performed pre-dose and at 1h, 2h, 4h and 6h post-dose on Day 29 (Week 4).

**Lipid profile:** at the study Visits 1, 2, 10 and 19 (Screening and study Weeks 0, 16, and 52) a blood sample will be collected for LDL, HDL and total cholesterol and Triglycerides testing.

**Clinical chemistry:** at the study Visits 1, 2, 7, 8, 10, 15, 16, and 19 (Screening and study Weeks 0, 4, 8, 16, 20, 28, and 52) a blood sample will be collected for sodium, potassium, chloride, calcium, magnesium, bicarbonate, phosphate, blood urea nitrogen, random glucose, albumin, total protein, alkaline phosphatase, creatinine, ALT, AST, gamma glutamyl transferase (GGT), total bilirubin, conjugated bilirubin testing.

**Coagulation profile:** at the study Visits 1, 2, 10, 16, and 19 (Screening and study Weeks 0, 16, 28, and 52) a blood sample will be collected for PT, INR, and aPTT testing.

**Serology:** at Screening visit a blood sample will be collected for: anti-VZV IgG, HIV antibodies, HBsAg, and HCV antibodies testing.

**QuantiFERON Gold test:** at Screening Visit a blood sample will be collected for TB antigens testing.

**Serum pregnancy test:** at Screening Visit a blood sample will be collected for serum beta-hCG testing.

The following tests will be performed at a clinic site:

**Urinalysis dipstick:** at the study Visits 1, 2, 10, and 19 (Screening and study Weeks 0, 16, and 52) a urine sample will be collected for pH, specific gravity, protein, glucose, ketones, and blood testing.

**Microscopic exam** may be performed at the local or central laboratory at the discretion of the Investigator if the dipstick is positive (i.e. trace or above).

**Urine Pregnancy Test:** at the [REDACTED] [REDACTED] a urine sample will be collected in women of childbearing potential for hCG testing.

A positive result should be confirmed by a serum beta-hCG test. A confirmed positive urine pregnancy test during the treatment periods of the study requires immediate interruption of study drugs and the subject must be discontinued from the study.

**C-reactive protein test (CRP):** Test for CRP will be done for all subjects. At the study Visits 2, 10, 16, and 19 (study Weeks 0, 16, 28, and 52) a blood sample will be collected for CRP testing.

**Rheumatoid Factor (RF):** may be performed at study visit 1 or 2 at the local or central laboratory at the discretion of the Investigator to establish if there is a diagnosis of PsA per the Classification of Psoriatic Arthritis (CASPAR) criteria.

[REDACTED]  
[REDACTED]

For Hematology, Chemistry profile the labs, which were abnormal and clinically significant at EOT, are needed at safety follow-up visit.

Hematology, chemistry (including lipid profile and CRP), coagulation and continuous urinalysis parameters and their changes from baseline will be summarized descriptively by visit and treatment group. For WBC and differentials (absolute counts and percentages) percent change from baseline will also be summarized.

Additionally, hematology (WBC and differentials) results obtained during Day 29 (Week 4) visit will be summarized by timepoint with changes and percent changes from pre-dose.

Shifts from baseline among the categories Normal (within the reference range), Low (below the reference range) and High (above the reference range) will be presented by visit.

In the analyses of change from baseline and shifts from baseline above, Part II baseline will be used for the groups that switched treatment in Part II, while Part I baseline will be used for the other treatment groups.

All results will be listed.

[REDACTED]  
[REDACTED]  
[REDACTED]

The number and percentage of subjects with pulse rate  $\leq 40$  bpm,  $\leq 50$  bpm and with decrease

In the analyses of change from baseline above, Part II baseline will be used for the groups that switch treatment in Part II, while Part I baseline will be used for the other treatment groups.

All ECG findings will be listed.

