- To evaluate the efficacy of SCD-044 in the treatment of Palmoplantar Psoriasis as measured by Palmoplantar Physician Global Assessment (PPPGA) score

Exploratory Objectives:

- To examine the pharmacodynamic/pharmacokinetic (PK/PD) relationship between SCD-044 plasma concentrations and PASI response
- [REDACTED]
- [REDACTED]
- To evaluate the effect of SCD-044 on subject reported outcome of itching associated with Psoriasis
- To evaluate the effect of SCD-044 on Psoriatic Arthritis (PsA)-related Pain (Patient Assessment of Pain (PtA-P))
- To evaluate the effect of SCD-044 on blood-based biomarkers.

Design:

Subjects in this randomized, double-blind, placebo controlled, parallel-group, multiple-center study will be assigned to treatment with the investigational products or placebo control according to a randomization scheme and titration schedule:

- **Part I:** 16 weeks: Subjects will be randomized to placebo, Low dose [REDACTED] Intermediate dose [REDACTED] or High dose [REDACTED] of SCD-044 [REDACTED]
[REDACTED]
[REDACTED]
[REDACTED]
[REDACTED] to assess primary and secondary endpoints at 16 weeks

Part II: Week 16 to Week 28:

At Week 16, subjects initially randomized to a treatment group will be re-randomized or discontinued from the study based on the PASI response as follows:

- Subjects initially randomized to placebo with a response of:

[REDACTED] will be re-randomized to Intermediate dose, High dose, [REDACTED]
[REDACTED]
[REDACTED] will be re-randomized to Intermediate dose or High dose [REDACTED]
[REDACTED]

- Subjects originally randomized to Low dose and Intermediate dose arms with a response of:

[REDACTED] will be switched to High dose [REDACTED]
[REDACTED]

[REDACTED] will remain on their assigned dosing regimen

- Subjects originally randomized to High dose arm with a response of:

[figure not shown]
[REDACTED]
[REDACTED] will remain on their assigned dosing regimen

Re-randomized subjects continuing in the study will stay on their assigned dosing regimen until the end of Part II (Week 28). [REDACTED]

[REDACTED]

[REDACTED]

- **Part III:** Week 28 to Week 52: Subjects with a response of [REDACTED] at Week 28 will be discontinued from the study. Subjects with a response of [REDACTED] at Week 28 will continue their existing dosing regimen until the end of Part III.

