S1PR1 modulation and the resulting lymphocyte sequestration have the potential for treating multiple autoimmune and chronic inflammatory diseases, including psoriasis. Ponesimod, another S1PR1 agonist has been found to be effective in the treatment of plaque psoriasis.¹¹

SCD-044 has shown efficacy in preclinical models of psoriasis. SCD-044 demonstrated a clinically meaningful reduction in lymphocyte counts with an acceptable safety profile in the Phase I study. The reduction in lymphocyte count is anticipated to result in therapeutic benefit in the treatment of psoriasis.

The current study is a Phase IIb dose ranging study to assess the efficacy and safety of SCD-044 in the treatment of moderate to severe plaque psoriasis.

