8. A query for PML (progressive multifocal leukoencephalopathy) will be performed (See Section 5.10)
9. A query for PRES (Posterior reversible encephalopathy syndrome) will be performed (See Section 5.11)
10. The Subject's body weight will be measured while the Subject is lightly clothed (e.g., no coat or shoes)
11. The Subject's diary provided at the previous visit will be collected and reviewed.
12. The returned study drugs will be counted
13. The use of concomitant medications since the previous study visit will be documented and assessed. (See Section 5.8)
14. A urinalysis dipstick will be performed and evaluated at a site (See Section 5.5)
15. A blood sample will be collected for Hematology, Lipid Profile, Chemistry, and Coagulation profile (See Section 5.5)
16. A blood sample will be collected for PD biomarkers sample (See Section 6.3)
17. A blood sample will be collected within one hour before dosing for PK testing (See Section 6.2)
18. A blood sample will be collected for C-reactive protein (CRP) – (See Section 5.5)
19. Independent Safety Assessor review:
 - Safety Lab Alerts
 - [REDACTED]
 - As available
 - i. Lab results
 - ii. Exam results
20. Study drug administration in a clinic before 12 noon (See Section 8.5)
21. [REDACTED]
[REDACTED]
[REDACTED]
22. A general safety review before discharge
23. On-site Visit 14 (Study Day 134 ±1 Day) will be scheduled and the Subject will be instructed to bring the Study Product (used, unused, and partially used packs), and Subject diary with him or her to this visit.
24. [REDACTED]
[REDACTED]
[REDACTED]

■ [REDACTED]
■ [REDACTED]
■ [REDACTED]

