9.7 Safety Assessment

Safety Assessments will include vital signs, physical examination, adverse events (AEs), laboratory tests, ECG monitoring, pulmonary function tests, ophthalmologic exams.

The safety of SCD-044 will be evaluated by:

- Incidence, seriousness and severity of all adverse events
- Shifts from baseline in hematology and laboratory tests
- Incidence of AEs of special interest (AE-SI)
- [REDACTED]
- [REDACTED]

The extent of exposure will be summarized using descriptive statistics. No inferential analyses are planned.

Incidence of all adverse events reported during the study will be summarized using the MedDRA dictionary by System Organ Class and Preferred Term, by treatment group, severity, and relationship to study drug.

An AE is considered treatment emergent if it was not present prior to the first dose of treatment or, if it was present, it worsened in severity or treatment attribution.

Safety analyses will be performed on the Safety Population. All safety data will be listed by treatment and subject in data listings. AEs will also be summarized by actual dose at time of onset of the AE to account for possible dose reductions over the course of the study.

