- Part II Baseline is defined as the last assessment, scheduled or not, prior to the first dose of the study drug in Part II. Part II baseline will be used in analysis of findings collected in Parts II, III and IV for subjects who were re-randomized in Part II to another treatment (i.e. SCD-044 [ ] or [ ] after being treated with Placebo in Part I or to SCD-044 [ ] after being treated with SCD-044 [ ] or [ ] in Part I). Throughout this SAP, if the word “baseline” is used without qualification “Part I” or “Part II”, it will refer to Part I baseline.

In by-visit summaries, only data collected on scheduled visits/timepoints will be summarized. Data from unscheduled assessments will be included in listings and may be used in determination of baseline if applicable.

Relative days will be calculated relative to date of first dose of the study drug. Relative days will be calculated as follows only when the full assessment date is known (i.e., partial dates will have missing relative days).

For assessment on or after the day of first dose of the study drug:

Relative Day = Date of Assessment – Date of First Dose of Study Drug+1.

For assessment before the day of first dose of the study drug:

Relative Day = Date of Assessment – Date of First Dose of Study Drug.

All dates will be displayed in DDMMYY format.

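### Laboratory change and shift results for low-to-high and intermediate-to-high switchers are measured only from an on-drug Week 16 baseline, so their cumulative change from before treatment is not reported and their columns do not compare with the other groups

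*SAP*

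**What the plan says.** The Protocol names "Shifts from baseline in hematology and laboratory tests" (9.7) among its safety evaluations, and its visible text does not mention a second baseline.

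The SAP introduces one. Under 6.1, "Part II Baseline is defined as the last assessment, scheduled or not, prior to the first dose of the study drug in Part II", and "Part II baseline will be used in analysis of findings collected in Parts II, III and IV for subjects who were re-randomized" to another treatment. The parenthesis that follows in 6.1 covers two kinds of subject: those who go from placebo to SCD-044, and those who go from one SCD-044 dose to another. The dose labels are redacted, but both routes are readable. Section 6.11.2 repeats the rule for laboratory change and "shifts from baseline above, Part II baseline will be used for the groups that switched treatment in Part II", with the Part I baseline for everyone else.

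The active-to-active route comes from the Protocol (synopsis and Section 3): some low-dose and intermediate-dose subjects "will be switched to High dose" at Week 16. The response cut-off is redacted.

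Section 6.11.2 also plans by-visit summaries of the parameter values themselves, shift tables among Normal, Low and High, percent change for WBC and differentials, and a listing of all results.

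**The concern.** A baseline for safety change should normally be free of the drug under study. For the two active-to-active groups it is not. The Protocol's introduction reports that "SCD-044 demonstrated a clinically meaningful reduction in lymphocyte counts" and expects benefit to come from that reduction, so a Week 16 lymphocyte count in these subjects is expected to be lowered already.

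Two things follow. First, the Part II-IV tables answer only how much more the laboratory values moved after the switch. They do not say how far these subjects are from where they started before treatment. Second, one table headed change from baseline would hold columns with different meanings: pre-drug for stayers, drug-free for placebo switchers, on-drug for active switchers. A reader comparing low-to-high switchers with subjects on high dose from the start could conclude that the switchers had milder changes when only the reference point differs.

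**Working it through.** The plan states no figure on this point, so there is none to reproduce. The check is a reading of the rule followed by an illustration.

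**Step 1: is the Week 16 value on-drug?** At Visit 10 (Protocol 7.1.6) returned study drug is counted, and "A blood sample will be collected for Hematology, Lipid Profile, Chemistry, and Coagulation profile". The visit is also when re-randomization is done and a dose is given in the clinic. No washout is described. For low-dose and intermediate-dose subjects the last laboratory value before the first Part II dose is therefore an on-treatment value.

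**Step 2: which reference point applies to each Part II-IV group?**

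| Group | Reference | Drug status at reference |
|---|---|---|
| Stays on one SCD-044 dose | Part I baseline | Pre-drug |
| Placebo to SCD-044 | Part II baseline | Drug-free |
| Low or intermediate to high | Part II baseline | On SCD-044 about 16 weeks |

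The sentence in 6.11.2 names change and shifts. Percent change is reached through the general rule in 6.1.

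**Step 3: effect on percent change.** Let r16 be the fall from the pre-drug value at Week 16 and r the fall at a later visit on high dose.

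- From the Part I baseline: change = -r.
- From the Part II baseline: change = (1 - r)/(1 - r16) - 1.

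Neither r nor r16 is given in the documents. Assumed values give the following changes from the Part II baseline:

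| Assumed r16 | r = 50% | r = 60% | r = 70% |
|---|---|---|---|
| 0% | -50.0% | -60.0% | -70.0% |
| 20% | -37.5% | -50.0% | -62.5% |
| 40% | -16.7% | -33.3% | -50.0% |
| 50% | 0.0% | -20.0% | -40.0% |
| 60% | not applicable | 0.0% | -25.0% |

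Example: r = 60%, r16 = 40% gives 0.40/0.60 - 1 = -33.3%, against -60% from the Part I baseline.

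**Step 4: effect on shifts.** This was simulated under further assumptions, none from the documents: log-normal lymphocyte count with pre-drug mean 2.0, between-subject CV 30%, within-subject CV 15%, lower limit 1.0 in the same units, true later fall 60%.

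| Assumed r16 | Low at later visit | Normal-to-Low, Part I baseline | Normal-to-Low, Part II baseline | Low-to-Low, Part II baseline |
|---|---|---|---|---|
| 20% | 79.2% | 76.8% | 69.5% | 9.7% |
| 40% | 79.1% | 76.7% | 45.8% | 33.4% |
| 50% | 79.2% | 76.7% | 25.6% | 53.6% |

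The total Low at the visit does not depend on the baseline. What changes is how many count as a new shift.

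**Step 5: can the cumulative result be recovered from other planned tables?** Not for these groups. Under SAP 6.1.1, data up to Week 16 are summarised by Part I arm, so subjects who later switch are pooled with those who stay or leave. Summary percent changes from two tables on different subjects cannot be chained. A Low-to-Low cell does not show whether the subject was Normal before treatment. The whole-study adverse event summary in 6.11.1 is confined to subjects who never switched, and no whole-study laboratory table for switchers is visible.

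**The case against.** A reader might infer that lymphocyte depletion and other abnormalities disappear from the Part II-IV safety tables. They do not. Section 6.11.2 tabulates actual values by visit and treatment group whatever the baseline, and these are directly comparable across groups. A subject who is Low at Week 16 and later appears in the Low-to-Low cell, the earlier Normal-to-Low shift is in the Part I tables, and every result is listed. Clinically significant abnormal laboratory findings are also adverse events (Protocol 5.9), and those summaries do not use this baseline. Switchers are shown by treatment sequence, not pooled with high-dose stayers. All of this stands and limits the point to change, percent change and new-shift results.

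It can also be said that Week 16 is a legitimate reference because it isolates the effect of the dose increase. That stands too, and it is why the Week 16 results should be kept. It does not answer the cumulative question.

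Redaction is a further limit. Text in and after 6.11.2 and in Protocol 9.7 is missing and may contain threshold-based laboratory summaries. Such summaries would help, but they would not alter the change and shift tables defined in the visible text.

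Two further inferences go beyond the documents. Liver injury is listed only as a known or potential class risk (Protocol 4.6), so it cannot be stated that liver values are already affected at Week 16. And the visible part of SAP 6.10 names no baseline for the biomarker analyses, so it cannot be said that the lymphocyte analysis in Protocol 9.12 is affected.

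**Conclusion.** The point holds in limited form. For low-to-high and intermediate-to-high switchers, Part II-IV laboratory change, percent change and shifts are measured only from an on-drug value. Any effect present at Week 16 is removed from those results, and their columns are not comparable with those of stayers or placebo switchers. That much follows from the text and needs no assumption.

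The size does need assumptions. With an assumed true lymphocyte fall of 60%, the reported change would be -50% to 0% for a Week 16 fall of 20% to 60%. Under the simulation's assumptions, Normal-to-Low shifts would drop from about 77% to about 70%, 46% or 26% for Week 16 falls of 20%, 40% or 50%. If the earlier dose had no effect by Week 16, there would be no distortion.

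This is a gap in descriptive safety tables. It does not touch the primary or key secondary efficacy analysis, and it does not support a claim that safety signals are concealed.

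**What to change.** In SAP 6.11.2, and consistently in 6.1:

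- For the low-to-high and intermediate-to-high groups, add Part II-IV laboratory change, percent change and Normal/Low/High shifts from the Part I (pre-drug) baseline. Use these when comparing with groups that stay on one dose.
- Keep the results from the Part II baseline alongside, labelled as the incremental effect of the dose switch.
- Keep the Part II baseline for the placebo-to-active groups.
- State the reference point in each column heading or footnote, and name percent change explicitly in the rule.
- List the second baseline in SAP section 8, which at present declares only the expanded handling of intercurrent events and the added DLQI endpoint.

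The data are already collected. The cost is SAP wording, a derivation flag and one extra column or table.
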